ANNEX 1. LIST OF STAND ALONE DOCUMENTS14

2. LIST OF ABBREVIATIONS

Abbreviation	Definition
ACR	American College of Rheumatology
AE	Adverse Event
ANA	Antinuclear Antibody
AS	Ankylosing Spondylitis
BASDAI	Bath Ankylosing Spondylitis Disease Activity Index
BASFI	Bath Ankylosing Spondylitis Functional Index
DMARDs	Disease-modifying Antirheumatic Drugs
EULAR	European League Against Rheumatism
GEP	Good Epidemiological Practice
GGP	Guidelines for Good Pharmacoepidemiology Practices
HLA-B27	Human Leukocyte Antigen B27
IEA	International Epidemiological Association
IEC	Independent Ethics Committee
IRB	Institutional Review Board
ISPE	International Society for Pharmacoepidemiology
ISPOR	International Society for Pharmacoeconomics and Outcomes Research
MTX	Methotrexate
NA	Not Applicable
NIS	Non-interventional Study
NSAIDs	Nonsteroidal Anti-inflammatory Drugs

Abbreviation	Definition
RA	Rheumatoid Arthritis
SpA	Apondyloarhtopathies

4. ABSTRACT

See [ANNEX 1](#).

5. AMENDMENTS AND UPDATES

Amendment number	Date	Protocol section(s) changed	Summary of amendment(s)	Reason
1	28 July 2021	Section 4 Abstract	Added back in to accept link	Administrative
		Throughout Document	Spelling errors	Administrative
		Section 6. Milestones	Updated to align with Study Report	Administrative

6. MILESTONES

Milestone	Planned date
Start of data collection	01 September 2020
End of data collection	01 October 2020
Final study report	01 September 2021

7. RATIONALE AND BACKGROUND

Spondyloarthropathy or spondyloarthritis refers to any joint disease of the vertebral column. As such, it is a class or category of diseases rather than a single, specific entity.¹

Non-vertebral signs and symptoms of degenerative or other not-directly-infected inflammation, in the manner of spondyloarthropathies, include asymmetric peripheral arthritis (which is distinct from rheumatoid arthritis), arthritis of the toe interphalangeal joints, sausage digits, Achilles tendinitis, plantar fasciitis, costochondritis, iritis, and mucocutaneous lesions. However, lower back pain is the most common clinical presentation of the causes of spondyloarthropathies; this back pain is unique because it decreases with activity.² *Spondyloarthropathies* have an increased incidence of HLA-B27, as well as negative rheumatoid factor and ANA.

Ankylosing spondylitis (AS) is a type of arthritis in which there is long-term inflammation of the joints of the spine. Typically, the joints where the spine joins the pelvis are also affected. Occasionally, other joints such as the shoulders or hips are involved. Eye and bowel problems may also occur. Back pain is a characteristic symptom of AS, and it often comes and goes. Stiffness of the affected joints generally worsens over time.³

Between 0.1% and 1.8% of people are affected with AS world wide.⁴ Onset is typically in young adults. Males are more often affected than females.⁴

There is no cure for ankylosing spondylitis. Treatments may improve symptoms and prevent worsening. Treatments may include medication, exercise, and surgery. Medications used include NSAIDs, steroids, DMARDs such as sulfasalazine, and biologic agents.⁵

8. RESEARCH QUESTION AND OBJECTIVES

The objective of this study was to evaluate the 1 and 7 years (long-term) adherence of SpA patients on Enbrel and the difference in efficacy between adherent and nonadherent groups.

9. RESEARCH METHODS

9.1. Study Design

- **Retrospective analysis** of patients with SpA that received etanercept from Baghdad Teaching Hospital (Rheumatology Center) from May 2012 through August 2019.
- **Primary objective:** 1 and 7 years adherence of SpA patients on Enbrel.
- **Secondary objective:** The difference in efficacy between the adherent group of patients (who continued Enbrel treatment) and the nonadherent group.

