9.2. Setting

Patients and Methods

Data was collected from the Baghdad Teaching Hospital rheumatology registry. It captured all patients who have been treated with biologic therapies managed in the rheumatology department. The decision to initiate and maintain the treatment was guided by the American College of Rheumatology (ACR) recommendations.

Study population

Patients included in the study met the American College of Rheumatology/European League Against Rheumatism (EULAR) 2019 criteria for SpA⁶, with at least 1 year of follow-up after starting their first biologic therapy. Exclusion criteria: patients previously or currently treated with other biological treatments.

Hypothesis

There was a small percentage of patients who adhered to Enbrel over 7 years, and there was no difference between the adherent and the nonadherent group in efficacy.

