9.3. Data Sources

Patients were identified from the rheumatology patient registry with a SpA diagnosis and information was obtained on patient demographics (age, gender), education-level (years), present smoking status, disease duration (years), current MTX and steroid therapy (yes/no), baseline BASDAI, and BASFI and last assessment of baseline BASDAI and BASFI.

Primary Outcomes: was the percentage of patients that have 7 year adherence on Enbrel.

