9.8. Limitations of the Research Methods

No missing data that could lead to bias was an identified limitation in this study.

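### The plan does not say what August 2019 bounds, and its simple 7-year percentage counts patients who cannot yet be observed for 7 years as not achieving adherence

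*Combined protocol and SAP*

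**What the plan says.** Section 9.1 describes a retrospective analysis of SpA patients who received etanercept at one centre "from May 2012 through August 2019". Its primary objective is "1 and 7 years adherence of SpA patients on Enbrel". Section 9.3 states that the primary outcome "was the percentage of patients that have 7 year adherence on Enbrel".

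Entry is much less demanding than the outcome. Section 9.2 takes patients "with at least 1 year of follow-up after starting their first biologic therapy", and sections 9.2.1 and 9.2.2 require one year on Enbrel. Nothing requires 7 years of potential follow-up.

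Section 6 starts data collection on "01 September 2020" and ends it one month later. Section 9.6 calculates the share of patients reaching 7-year adherence as a percentage. It also compares the adherent and nonadherent groups on change in BASDAI and BASFI to an undated last visit. It names no follow-up cut-off, denominator restriction, censoring rule or time-to-event method. On limitations, section 9.8 says: "No missing data that could lead to bias was an identified limitation in this study".

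**The concern.** A 7-year outcome can be determined for a patient still on treatment only if the treatment started at least 7 years before observation ended. The window in 9.1 is barely longer than that, and the plan does not say whether it limits starts or observation. A patient who started in 2016 and is still on Enbrel at the cut-off has neither reached nor failed the 7-year outcome. A plain percentage over all included patients puts that patient in the denominator and never in the numerator.

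Two results are at stake. The primary percentage is biased downward, in the direction of the hypothesis in 9.2 that few patients adhere over 7 years. If the secondary comparison splits patients by 7-year status, patients still on treatment are also classed as nonadherent, which mixes them with patients who stopped.

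**Working it through.** The plan gives no figure to reproduce: no sample size, number of starters or expected adherence. The check is calendar arithmetic.

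**Inputs.** Window May 2012 to August 2019 (9.1); outcome horizon 7 years = 84 months (9.3); minimum time on Enbrel 1 year = 12 months (9.2.1); data collection 1 September to 1 October 2020 (section 6). Assumptions not in the documents: starts are spread evenly, and no included patient started before May 2012.

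**Reading A: August 2019 ends follow-up.**
- Window with both end months counted in full: 88 months.
- Start months that allow 7 years: 88 − 84 = 4 (latest start 31 August 2012).
- Start months that allow the required year: 88 − 12 = 76 (latest start 31 August 2018).
- Share observable to 7 years: 4/76 = 5.3%. In days, 122/2,313 = 5.3%.
- The exact first and last days are not given. The shortest case leaves 2 of 74 months, about 3%.
- Gap from 31 August 2019 to data collection: 367 days to 1 September 2020, 397 days to 1 October 2020.

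**Reading B: August 2019 ends starts, and follow-up runs to data collection.**
- A start on 31 August 2019 completes its required year on 31 August 2020, one day before data collection opens.
- May 2012 to 1 September 2020 is 100 months, so 100 − 84 = 16 start months allow 7 years (latest start 1 September 2013).
- Share observable to 7 years: 16/88 = 18.2%. In days, 488/(2,313 + 365) = 488/2,678 = 18.2%.
- Depending on exact days, the range is 15 of 87 to 17 of 88 months, about 17% to 19%.

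**Effect on a plain percentage over all included patients.** Only the observable share can enter the numerator, so

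reported percentage = observable share × true 7-year adherence among those patients.

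- Ceiling, with true adherence of 100%: 5.3% under A, 18.2% under B.
- With true adherence of 30% (assumption): 0.053 × 30% = 1.6% under A, and 0.182 × 30% = 5.5% under B.

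**Effect of a later cut-off under reading A.** For the same entrants (starts to 31 August 2018), moving the cut-off to 1 September 2020 raises the observable share from 122/2,313 = 5.3% to 488/2,313 = 21.1%. That is 488/122 = 4.0 times as many patients. For a proportion calculated only in patients with 7 years of potential follow-up, the 95% half-width shrinks by √(122/488) = 0.5, whatever the cohort size or proportion. As an illustration, take 200 entrants and a 30% proportion (both assumptions), with half-width 1.96 × √(0.21/n):
- n = 10.5 gives 27.7 percentage points.
- n = 42 gives 13.9 percentage points.

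The first rests on about 3 adherent patients, so the normal approximation is rough. Both figures describe a complete-case proportion. They do not measure the gain in a Kaplan-Meier estimate, to which later starters also contribute.

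**The case against.** The strongest reply is that no section calls August 2019 a follow-up cut-off. Section 9.1 says who is studied, and the only end of follow-up in 9.6 is an undated last visit. If the window bounds starts, the required year for the last starter ends just as data collection opens, which fits the milestones well. On that reading follow-up already runs to September 2020. This stands. A reader might infer that only the first four months of starters can ever count, or that a year of existing follow-up is discarded. The documents support neither as fact. The first holds only under reading A. The second also needs the registry to hold visits after August 2019, which no section says. Against this, 9.1 dates the receipt of etanercept and not its start, so reading A cannot be excluded either.

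A second reply is that the remedy may not be cheap. The protocol is largely in the past tense, its July 2021 amendment aligned the milestones with the study report, and sections 10 and 11 describe anonymized data without retrieval of individual patient data. Whether the same patients can be linked to later visits is unknown. This too stands, and it limits the fix to what the registry holds.

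A third reply is that the end of observation is not a missing registry entry, so 9.8 is not contradicted. That is fair. Section 9.8 does not claim 7 years of follow-up for everyone. Nor does it deal with the fact that 7-year status is undetermined for patients still on treatment.

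Finally, 9.1 describes the adherent group as those who continued Enbrel, which could put continuing patients on the adherent side of the secondary comparison. Section 9.6 does not say whether that description or 7-year status defines the groups, so the risk of misclassification remains.

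None of these replies supplies a denominator or a censoring rule for the primary outcome.

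**Conclusion.** The point holds in conditional form. The plan leaves open what August 2019 bounds, and it gives no follow-up cut-off. With even starts and none before May 2012, the start dates that cannot be observed to 7 years are about 95% of those eligible if August 2019 ends follow-up, and about 82% if it ends starts and follow-up runs to September 2020. Uneven accrual would change these shares. More starters early in the window would raise the observable share, and more late starters would lower it.

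The main defect does not depend on the reading. A plain percentage over all included patients is biased downward, with a ceiling of about 5% or 18%. Splitting the efficacy groups by 7-year status would place patients still on treatment among the nonadherent. A later cut-off alone does not cure this, because most starters would still have less than 7 years of potential follow-up.

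A reader might also infer that a later cut-off halves the uncertainty of the primary result. That is shown only for a complete-case proportion under reading A. Any precision gain for the recommended analysis should be given as a range under stated assumptions.

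**What to change.** - **Section 9.1:** say whether August 2019 closes treatment starts or follow-up. State that follow-up for Enbrel status and for the last BASDAI and BASFI runs to the registry extraction date, or to the last date with complete visit recording if that is earlier.
- **Section 9.6, primary outcome:** estimate 7-year adherence by Kaplan-Meier with administrative censoring at that date, conditional on the required first year on Enbrel. Show the number at risk, since few patients will be under observation near 7 years. State the assumption that early and late starters stop at similar rates.
- **Alongside it:** report the plain percentage among patients with 7 years of potential follow-up, with its denominator.
- **Sensitivity analysis:** repeat with the August 2019 cut-off.
- **Section 9.6, secondary comparison:** say how patients still on Enbrel with less than 7 years of observation are classified, so that they are not counted as nonadherent by default.

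**Cost.** Changed wording, a re-analysis and, if the registry holds visits after August 2019, a longer extract on the same patients, with a check that the added period is completely recorded. Section 9.3 does not list Enbrel start and stop dates among the items obtained, so the extract must include them. No new patients are needed. If the anonymized records cannot be linked to later visits, the censored analysis can still be run to the last date that the existing data cover.

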9.2.1. Inclusion Criteria

Patients met all of the following inclusion criteria to be eligible for inclusion in the study:

1. Diagnosed SpA patients.
2. 18 years of age and older.
3. Did not receive previous other biological treatments.
4. Patients have at least 1 year on Enbrel.

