9.6. Data Analysis

All covariates will be summarized to get information about frequency distribution and mean, median or standard deviation. Numbers and percentages will be provided for dichotomous and polychotomous variables when performing descriptive analysis of categorical data. Means, medians, standard deviations, and interquartile range as appropriate will be provided for continuous variables when performing descriptive analysis of continuous data. Patients will be assessed for first-year adherence (first-year adherence is defined as patients having at least 7 consecutive visits in one year of Enbrel treatment), then the 7-year adherence will be assessed and the percentage of patients that achieve 7-year adherence will be calculated. The difference between adherent and nonadherent groups in baseline visit and last visit BASDAI and BASFI will be assessed for both groups.

The bivariate analysis will be conducted to determine if there is any association between the outcome and the exposure (the covariates). Unadjusted comparisons between groups of covariates and outcomes will be evaluated using appropriate tests: chi-squared test will be used for categorical variables, t-test will be used for continuous variables, and the Kruskal-Wallis test for non-parametric variables; p-values will be generated. The baseline variables considered demographic data, disease duration (years), methotrexate (yes/no), current steroid therapy (yes/no), present smoking (yes/no).

The difference in efficacy between adherent and nonadherent groups by using change from the baseline in BASDAI and BASFI at the last visit will be determined. P-value <0.05 will be considered statistically significant, without multiplicity adjustment for this post-hoc analysis.

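### The efficacy groups are not fixed: section 9.1 groups by continued Enbrel use, sections 9.2 and 9.6 point to a 7-year split, and that split counts patients still on Enbrel with under 7 years of follow-up as nonadherent

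*Combined protocol and SAP*

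**What the plan says.** Section 9.1 (Study Design) gives the secondary objective as "The difference in efficacy between the adherent group of patients (who continued Enbrel treatment) and the nonadherent group". The bracket describes the adherent group by continuation and sets no duration.

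The efficacy hypothesis in section 9.2 (Setting, Hypothesis) expects "a small percentage of patients who adhered to Enbrel over 7 years, and there was no difference between the adherent and the nonadherent group". The 7-year criterion and the efficacy statement share one sentence.

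Section 9.3 names the primary outcome: it "was the percentage of patients that have 7 year adherence on Enbrel".

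Section 9.6 (Data Analysis) defines first-year adherence by a visit count, and "then the 7-year adherence will be assessed and the percentage of patients that achieve 7-year adherence will be calculated". The next sentence compares adherent and nonadherent groups on BASDAI and BASFI, and a later one uses change from baseline at the last visit. Neither says which adherence definition forms the groups.

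Entry under section 9.2.1 requires only this: "Patients have at least 1 year on Enbrel". Section 9.1 covers patients who received etanercept "from May 2012 through August 2019". No section says how to classify a patient who is still on Enbrel with less than 7 years of follow-up.

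**The concern.** The two descriptions put the same patient in opposite groups. Someone who started in 2016 and was still treated in August 2019 continued Enbrel, so is adherent under 9.1. The same person has not completed 7 years, so is nonadherent under a 7-year split.

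The secondary question is whether patients who continued Enbrel fare better than those who did not. If part of the comparator is still taking the drug, the contrast no longer answers that question. When those patients do better than stoppers, the estimate moves toward zero, which is what 9.2 hypothesises. A non-significant p-value could then be misread as equal efficacy in continuers and stoppers.

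Handling censoring properly in the primary percentage would not repair this, because the efficacy groups are formed separately.

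**Working it through.** The plan gives no sample size, effect, accrual pattern or stopping rate, so there is no figure of its own to reproduce. The check has a calendar part and an illustrative part.

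**1. Calendar (from 9.1 and 9.2.1).** The window runs from the start of May 2012 to the end of August 2019: 88 months, T = 7.33 years. Taking first use as no earlier than May 2012, 7 years by the end of August 2019 requires a start by about the end of August 2012. Later starters cannot reach 7 years even if they never stop.

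**2. Effect on the contrast.** Let A, C and B be the mean changes in 7-year adherers, patients still on Enbrel with under 7 years, and stoppers. Let m be the share of the nonadherent group still on Enbrel. Then

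observed contrast = A − [mC + (1 − m)B] = (A − B) − m(C − B).

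If C = A, this is (1 − m)(A − B). Illustration with A = −3, B = −1.5 (true contrast −1.5) and m = 0.6:
- C = −3 gives −0.6.
- C = −2.5 gives −0.9.
- C = −1.5 gives −1.5 (no dilution).
- C = −1.0 gives −1.8 (the gap widens).

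**3. Size of m, even starts, August 2019 cut-off.** Assumptions not in the documents: starts spread evenly up to 1 year before cut-off, no stopping in year 1 (from eligibility), then a constant annual stopping rate h, with λ = −ln(1 − h).

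- 7-year adherers: P = [(T − 7)/(T − 1)] × (1 − h)^6, where (T − 7)/(T − 1) = 0.333/6.333 = 5.3% is the share able to reach 7 years.
- Still on drug with under 7 years: Q = [1 − (1 − h)^6] / [λ(T − 1)].
- m = Q/(1 − P).

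| h | P | Q | m | Contrast kept if C = A |
|---|---|---|---|---|
| 10% | 0.028 | 0.702 | 0.72 | 28% |
| 20% | 0.014 | 0.522 | 0.53 | 47% |
| 30% | 0.006 | 0.391 | 0.39 | 61% |

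**4. Later cut-off.** Section 6 ends data collection on 01 October 2020. If follow-up runs to then, about 19–22% of start dates can reach 7 years. The value of m is about 0.65–0.67, 0.45–0.47 and 0.32–0.34 at the same stopping rates. The ranges reflect whether starts are capped at August 2019.

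**5. Front-loaded starts, August 2019 cut-off.** Let half of patients start in the first 4 months and spread the other half evenly as in step 3. About 53% can then reach 7 years (0.5 + 0.5 × 0.053). P becomes 0.5 × (1 − h)^6 plus half of the P in step 3, and Q is halved. At h = 10%, P = 0.266 + 0.014 = 0.280, Q = 0.351 and m = 0.351/0.720 = 0.49. At 20% and 30%, m = 0.30 and 0.21.

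**6. Power, illustration only.** Assume 200 patients, SD 2, a true difference of 1 point, even starts and an August 2019 cut-off. Power (two-sided 5%, normal approximation) is about 6–7% with the 7-year split and 88–94% with continued versus stopped, for 10–20% stopping. Group size explains much of this gap. The 7-year group has 200 × 0.028 = 5.6 patients at 10% stopping and 200 × 0.0138 = 2.8 at 20%. With no dilution, z = 1/[2√(1/5.6 + 1/194.4)] = 1.17, so power is about 21%. At 20% stopping, z = 0.82 and power is about 13%. A normal approximation is also unreliable with so few patients in one group.

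**The case against.** The strongest reply is that the plan never commits to the 7-year split. The one place that describes the efficacy groups, 9.1, already uses continuation. The only operational adherence rule, in 9.6, is for the first year, and a first-year split would not produce this contamination. On that view the fault is an undefined term. This stands as far as it goes: a reader might infer that the plan has chosen the 7-year split, and the documents do not establish that. They do lean that way in 9.2 and in the order of 9.6, nothing rules the split out, and using it would contradict 9.1. That is more than missing detail.

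A reader might also infer that most eligible patients cannot reach 7 years. Only the date limit is arithmetic. The share of patients affected rests on start dates that the documents do not give, and under the front-loaded pattern about half could reach 7 years.

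Third, the direction is an inference. No document reports outcomes by group. There is no dilution if patients still on drug change as much as stoppers, and the gap widens if they do worse. So the documents do not support saying that the design confirms no difference by construction.

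Finally, the power loss cannot be put down mainly to on-drug patients in the comparator. Even without dilution, power in the example is only about 21% and 13%.

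**Conclusion.** The concern holds in conditional form. Sections 9.1, 9.2 and 9.6 do not agree on what makes a patient adherent for the efficacy comparison. If the 7-year split is used, patients still on Enbrel who started after about August 2012 join the comparator when follow-up ends in August 2019.

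For assumed stopping of 10–30% per year and that cut-off, they make up about 72–39% of the nonadherent group with even starts, and about 49–21% if half of patients start in the first 4 months. The contrast kept is then 28–61% or 51–79%, but only if patients still on drug have the same mean change as 7-year adherers. The shrinkage itself needs them to do better than stoppers. These figures illustrate scale and do not estimate the bias in this study. The power comparison should be read as illustration only.

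This affects the secondary objective and should be corrected before the efficacy result is interpreted.

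**What to change.** - In 9.1, 9.2 and 9.6, define the efficacy groups as continued (still on Enbrel at the data cut-off or last recorded visit) versus stopped (recorded discontinuation on or before cut-off). State the cut-off date.
- State that no patient still on Enbrel is nonadherent only because follow-up is under 7 years.
- Give a classification rule for patients lost to follow-up without a recorded stop, and for patients who stop after completing 7 years. The latter meet the primary outcome yet would fall in the stopped group.
- Add Enbrel stop date or last-treatment date to the variables in 9.3. It is not listed there, although the primary adherence outcome needs it.
- Report any 7-year efficacy contrast as supplementary, with both groups limited to patients who started at least 7 years before cut-off.

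The cost is about one sentence in each of 9.1, 9.2 and 9.6, two classification rules, one added variable and a recoded grouping. No new patients are needed. If treatment dates were not in the extract, they would have to be obtained from the registry, and the documents do not say whether that is possible.

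There are two downsides. The result would describe continued versus stopped use, not 7-year adherers. It would also remain confounded, because stopping may depend on response, so it should be interpreted as an association.
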